#### **5.4. Open-label Extension (OLE) Clinical Assessment Endpoints in Part 2**

The following endpoints will be assessed during the OLE:

- Proportion of subjects with pain-free status at 2-hour postdose for each treated migraine headache that reached moderate to severe intensity. These descriptive summaries will be presented at each visit by weight group and dose during the OLE. If a subject did not experience a treated migraine headache between visits, he or she will be excluded in the summary for that particular visit.

- Change from randomization in the PedMIDAS total score will be summarized descriptively at the end of the study by weight group and dose based on the last dose received in the study.
- Proportion of subjects experiencing 2-hour pain free for  $\geq 20\%$ , 40%, 60%, and 80% of their treated moderate to severe migraine headaches. For each subject the proportion will be calculated as  $[\text{Number of migraine headaches treated with the given dose level resolving to pain-free in 2 hour}]/[\text{Number of all migraine headaches treated with the given dose level}] * 100\%$ . For subjects who received different dose levels or changed weight groups in the course of Part 2 of the study, the proportion will be calculated separately for each weight group and dose level.
- Proportion of treated moderate to severe migraine headaches that reduce to pain free at 2 hours:
  - o Descriptive summaries (mean, SD, median, min, max)
  - o Categorical summaries of  $\geq 20\%$ , 40%, 60%, and 80% of treated headaches

### **5.5. Changes From Protocol-Specified Efficacy Analyses**

If a subject naps or sleeps within 2 hours after dosing with study drug for a particular treatment period, the subject will be considered a non-responder for all diary time points up to and including the 2-hour diary time point for that treatment period.

The randomized population is replaced by the full analysis set. The completers population is further clarified as the double-blind completers analysis set.

The protocol inadvertently states that the McNemar's test was to be performed for Period 1 data. This SAP has corrected that the McNemar's test will be performed for each sequence.

Additional endpoints were added to the OLE endpoints to further elucidate the effect of ZNS:

- Proportion of subjects experiencing 2-hour pain free for  $\geq 20\%$ , 40%, 60%, and 80% of their treated moderate to severe migraine headaches.
- Proportion of treated moderate to severe migraine headaches that reduce to pain free at 2 hours:
  - o Descriptive summaries (mean, SD, median, min, max)
  - o Categorical summaries of  $\geq 20\%$ , 40%, 60%, and 80% of treated headaches

## **6. SAFETY ANALYSES**

### **6.1. Adverse Events and Deaths**

#### **6.1.1. Adverse Event Dictionary**

Reported AEs will be coded to standard terms using a standard dictionary (Medical Dictionary for Regulatory Activities [MedDRA]) latest version at the time of the database finalization.

#### **6.1.2. Adverse Event Severity**

Severity of adverse events will be determined by the investigator as mild, moderate, or severe. AEs with missing severity will be queried to resolution.

#### **6.1.3. Relationship of Adverse Events to Study Drug**

Related AEs are those for which the investigator selected “Related,” “Possibly Related,” or “Unlikely Related” on the AE case report form (CRF) to the question of “Relationship to Study Treatment.” Relatedness will always default to the investigator’s choice, not that of the medical monitor. AEs with missing relationship to study drug will be queried to resolution.

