## 1.2. Sample Size and Power

Part I of this study is a randomized, double-blind, placebo-controlled, 2-period, crossover outpatient study with a 6-week placebo run-in period.

Approximately 426 subjects will be enrolled to the placebo run-in period to randomize 288. With the 5:1 (high dose:low dose) randomization ratio for each of the two weight strata, it is estimated that 240 subjects will be randomized in the high-dose group and 48 subjects will be randomized to the lower dose level.

The sample size is based on detecting a difference in the percentage of subjects treated with a high dose (2.5 mg in the <50 kg weight stratum and 5 mg in the ≥50 kg weight stratum) who are pain free at 2 hours between ZNS and placebo. In this crossover trial, 240 high-dose-treated subjects will be adequate to detect a clinically relevant difference of 0.11 in the percentage of subjects who are pain free at 2 hours between ZNS and placebo as statistically significant (0.05, two tailed) with 90% power assuming a standard deviation of 0.5.

Approximately 48 subjects will be randomized in the low dose level (1 mg in the <50 kg weight stratum and 2.5 mg in the ≥50 kg weight stratum). The data from the low dose level will be summarized to explore dose-response relationship.

Based on other migraine crossover studies, dropout rates during the placebo run-in period ranged from 12% to 50%. Based on this, approximately 426 subjects will be enrolled into the placebo run-in period to randomize 288. This allows for approximately 32% dropout during placebo run-in period.

Approximately 100 subjects who complete the double-blind crossover phase will enter the 6-month OLE to enable at least 50 subjects to complete at least 6 months treating on average at least one migraine attack per month (treating up to 4 migraine attacks per month) with ZNS. Part II of the study is an OLE with subjects who successfully complete Part I of the study.

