#### **6.1.5. Treatment-emergent Adverse Events**

Treatment-emergent adverse events (TEAE) are defined as events with an onset date on the date of a study drug administration and up to 3 days after that date. If in the OLE period a second dose of study drug is administered within 72 hours of the start of the migraine headache, the window for TEAEs is extended by 3 more days. A worsening of previous illnesses or experience from baseline while on study drug is also considered a TEAE.

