### **6.1.7. Summaries of Adverse Events and Deaths**

TEAEs will be summarized based on the safety analysis set for Part 1 and based on the OLE analysis set for Part 2. All TEAEs will be summarized by body system, and by preferred terms within a body system, by severity, and by relation to study medication. Each AE (based on preferred terminology) is counted only once for a given subject within a specified treatment or study period. If the same AE occurred on multiple occasions, the highest severity and least complimentary relationship will be assumed. If two or more AEs were reported as a unit, the individual terms will be reported as separate AEs.

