## **6.9. Changes From Protocol-Specified Safety Analyses**

There are no changes from the protocol-specified safety analyses.

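### SAP 6.1.3 pools 'Unlikely Related' adverse events with related ones, without a reason or a narrower summary, so related-event rates may be overstated, mainly in the open-label extension

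*SAP*

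**What the plan says.** - **Definition (SAP 6.1.3).** "Related AEs are those for which the investigator selected “Related,” “Possibly Related,” or “Unlikely Related". All three CRF answers feed one class of related events.
- **Whose answer counts (SAP 6.1.3).** "Relatedness will always default to the investigator’s choice, not that of the medical monitor".
- **Use (SAP 6.1.7).** All treatment-emergent adverse events (TEAEs) are summarised by body system and preferred term, "by severity, and by relation to study medication". This applies to the safety analysis set in Part 1 and to the OLE analysis set in Part 2. When the same event recurs in a subject, "the highest severity and least complimentary relationship will be assumed".
- **Window (SAP 6.1.5).** TEAEs are "events with an onset date on the date of a study drug administration and up to 3 days after that date", with 3 more days if a second OLE dose is taken for the attack.
- **Departures from the protocol (SAP 6.9).** "There are no changes from the protocol-specified safety analyses".

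No section explains the grouping, limits it, or adds a summary without *Unlikely Related*.

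**The concern.** An investigator who chooses *Unlikely Related* is saying that the drug probably did not cause the event. Under 6.1.3 that event joins the same class as one judged *Related*. In children aged 6 to 11, much of what is judged unlikely would be ordinary intercurrent illness, at a rate that does not depend on treatment.

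The consequence differs by study part. In Part 1 a similar background would be added under ZNS and under placebo, which pulls the ratio of related-event rates towards 1. In the OLE everyone receives ZNS, so the background goes straight into the reported related rate and a reader cannot subtract it. Safety is part of the primary objective (SAP 1.1), so it matters that these tables can be read as intended.

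**Working it through.** **No figure to reproduce.** The SAP states no rate, error level, power or sample size that depends on this definition. The check is a reading of Sections 6.1.1 to 6.1.7 and 6.9, plus an illustration of direction.

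**Reading the sections together**

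1. 6.1.3 sets the class, 6.1.7 uses it, and neither these sections nor 6.9 narrows it.
2. The worst-relationship rule in 6.1.7 adds a little. A subject becomes a related case for a term through an *Unlikely Related* occurrence only if every other occurrence of that term fell outside the 6.1.3 class. For most subjects the rule changes nothing.

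**Illustration for Part 1 (all rates assumed)**

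Let p be the proportion of subjects with a *Related* or *Possibly Related* event, and b the proportion with an *Unlikely Related* event. Assume that b is the same under ZNS and placebo and independent of p. The pooled proportion is

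p' = 1 − (1 − p)(1 − b).

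The difference becomes (p_ZNS − p_placebo)(1 − b), so it shrinks only by the factor 1 − b. The ratio can fall much further.

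| Assumed p, ZNS vs placebo | b | Pooled, ZNS vs placebo | Difference (points) | Ratio |
|---|---|---|---|---|
| 10% vs 3% | 0 | 10.0% vs 3.0% | 7.0 | 3.33 |
| | 2% | 11.8% vs 4.9% | 6.9 | 2.39 |
| | 5% | 14.5% vs 7.9% | 6.7 | 1.85 |
| | 10% | 19.0% vs 12.7% | 6.3 | 1.50 |
| 20% vs 5% | 0 | 20.0% vs 5.0% | 15.0 | 4.00 |
| | 2% | 21.6% vs 6.9% | 14.7 | 3.13 |
| | 5% | 24.0% vs 9.8% | 14.3 | 2.46 |
| | 10% | 28.0% vs 14.5% | 13.5 | 1.93 |

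Example for the second row: 1 − 0.90 × 0.98 = 0.118 and 1 − 0.97 × 0.98 = 0.0494. The difference is 0.0686 and the ratio 0.118/0.0494 = 2.39.

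**How much room the TEAE window leaves for background illness**

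- *Part 1.* One attack is treated per double-blind period (SAP 1.1). The dosing date plus 3 days gives 4 calendar dates per treatment.
- *OLE, one attack per month for 6 months* (the average that SAP 1.2 aims for): 6 × 4 = 24 dates, if windows do not overlap.
- *OLE, at the limit of 4 attacks per month:* 24 × 4 = 96 dates, again without overlap, and more with second doses.

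The OLE window can therefore be 6 to 24 times as long as the window for one double-blind treatment, with no comparator.

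**The case against.** The strongest defence is that the grouping is a cautious convention. It counts as related any event for which the investigator left a causal link open, however remote, so it errs towards over-reporting. All TEAEs are tabulated whatever their relationship, so no event disappears. The table shells, which SAP 2.2 refers to, are not at hand and may already show each CRF category. The protocol is not at hand either, and given 6.9 the grouping may come from it. All of this stands. It is why replacing the cut-point outright would be debatable, and why the point is low priority. It does not supply the missing reason or the missing narrower summary.

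Three stronger readings are tempting, and the SAP does not support them:

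- **That 6.1.3 contradicts itself.** A reader might set the sentence on the investigator's choice against the grouping. That sentence only decides between investigator and medical monitor. The investigator's entry is kept as recorded and then pooled.
- **That a test or interval loses strength.** A reader might compute a z-statistic on related events and see it fall. SAP 6.1.7 plans summaries only. Nor is the figure in SAP 1.2, "it is estimated that 240 subjects will be randomized in the high-dose group", a planned safety column, because SAP 2.1.1 and 2.2 split the summaries by dose and weight group. A two-sample formula would also ignore the crossover pairing.
- **That the drug-related signal is shown to be blunted.** The absolute difference hardly moves, the short window limits background illness in Part 1, and any size rests on rates that the SAP does not give.

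**Conclusion.** The point holds in a limited form. As written, 6.1.3 reports as related some events that the investigator considered unlikely to be due to the drug, without a reason and without a narrower count beside it. The direction is clear: related rates can only rise, most consequentially in the OLE, and a background that is equal under both treatments pulls the Part 1 ratio towards 1.

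The size cannot be determined from the document. The ratios in the table rest on assumed rates, equal background under both treatments, and independence of the two kinds of event. They show direction and plausible range and predict nothing. No efficacy result, error rate, sample size or planned test is affected. Priority: low.

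**What to change.** In 6.1.3, 6.1.7 and the table shells, present *Related* plus *Possibly Related* as a count and show *Unlikely Related* in its own column, for Part 1 and for the OLE. If the broad grouping is deliberate or comes from the protocol, keep it as an additional conservative summary and state the reason in 6.1.3. If the shells already separate the categories, a sentence in 6.1.7 saying so is enough.

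The data are already on the CRF. The cost is a short text change and one more column or table. The downside is that a less conservative narrow figure appears beside the broad one. Showing both keeps every event visible.

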#### **6.1.4. Serious Adverse Events**

Serious adverse events (SAEs) will be identified and captured as SAEs if AEs met the definitions of SAE specified in the study protocol. Serious adverse events captured and stored in the clinical database will be reconciled with the SAE database from the Drug Safety database before data finalization.

#### **6.1.5. Treatment-emergent Adverse Events**

Treatment-emergent adverse events (TEAE) are defined as events with an onset date on the date of a study drug administration and up to 3 days after that date. If in the OLE period a second dose of study drug is administered within 72 hours of the start of the migraine headache, the window for TEAEs is extended by 3 more days. A worsening of previous illnesses or experience from baseline while on study drug is also considered a TEAE.

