Subjects who successfully complete the double-blind portion of this study and continue to be eligible will be offered participation in a 6-month outpatient open-label safety extension (OLE; Part 2) where they will treat up to 4 moderate to severe migraine attacks per month with ZNS. The occurrence, continuance, or recurrence of migraine headache pain for up to 72 hours after the onset of a migraine attack is considered to be part of this attack and is not considered a separate attack, regardless of treatment. Headaches occurring while the child is at school will not be treated with study drug. During the OLE, subjects will assess their pain-free status immediately prior to treatment with ZNS and 2 hours after the first dose for each migraine attack treated with ZNS. Subjects who do not obtain satisfactory relief of migraine pain by 2 hours after taking study drug, or if the headache recurs after 2 hours, are permitted to treat with a second dose of their study drug and/or their protocol-allowed pre-study acute migraine medication (eg, NSAIDs or acetaminophen). For each migraine attack, diary entries will only be made for the first dose of study drug; a second dose of study drug may not be administered within 2 hours of the first dose and no more than 2 doses of study drug are permitted within a 24-hour period and for any single attack. Other triptans and ergot derivatives are prohibited for 24 hours following the last dose of study drug treatment. Migraine-associated disability, using the PedMIDAS questionnaire, will be assessed at the end of study.

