## **2.7. Data Handling Conventions and Transformations**

Selected by-subject listings will be presented for all subjects in the safety analysis set and sorted by subject ID number, treatment period, and study day (if applicable). Data collected on log forms, such as AEs and concomitant medications, will be presented in chronological order by preferred terms within subject.

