#### **6.1.6. Assignment of Adverse Events to Study Parts and Treatment Groups**

Each treatment-emergent adverse event by definition occurs within 3 days (with a possible extension if a second dose was taken in the OLE period) of a study drug dose. TEAEs will be assigned to study parts based on the dose they are thus associated with, i.e. TEAEs occurring after run-in or double-blind doses will be assigned to Part 1 and TEAEs occurring after OLE doses will be assigned to Part 2. TEAEs will also be assigned to the treatment group associated with the dose.

Non-treatment-emergent AEs will be assigned to study parts based on their onset date. Non-treatment-emergent AEs starting prior to the date of Visit 4 will be assigned to Part 1 and starting on or after the date of Visit 4 to Part 2. In case an AE has a partial start date that is ambiguous

and could have occurred either before or after the date of Visit 4, such AE will be assigned to Part 1. Non-treatment-emergent AEs will not be assigned to treatment groups.

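### The SAP specifies adverse event summaries only for events starting within a few days of a dose, so later new events in the 6-month safety extension, including SAEs and deaths, reach only the listings

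*SAP*

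**What the plan says.** All references are to the SAP.

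- **Window (6.1.5).** TEAEs are "events with an onset date on the date of a study drug administration and up to 3 days after that date". If a second OLE dose is taken within 72 hours of the start of the migraine, "the window for TEAEs is extended by 3 more days". A further limb has no stated number of days: "A worsening of previous illnesses or experience from baseline while on study drug is also considered a TEAE".
- **Summaries (6.1.7).** "TEAEs will be summarized based on the safety analysis set for Part 1 and based on the OLE analysis set for Part 2". They are broken down by body system, preferred term, severity and relationship. The heading also names deaths, but the text does not mention them. Seriousness is not among the breakdowns.
- **Everything else (6.1.6).** "Non-treatment-emergent AEs will be assigned to study parts based on their onset date", but "Non-treatment-emergent AEs will not be assigned to treatment groups".
- **SAEs (6.1.4).** This section says how they are identified and reconciled with the safety database, not how they are summarised.
- **Listings (2.7).** "Data collected on log forms, such as AEs and concomitant medications, will be presented in chronological order by preferred terms within subject".
- **Setting (1.1, 1.2).** Part 2 is a "6-month outpatient open-label safety extension" in which up to 4 attacks a month may be treated. It is sized so that at least 50 subjects complete 6 months with an average of one or more treated attacks per month.

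**The concern.** A window of a few days after dosing suits a single treated attack in the crossover. The same rule also governs Part 2, whose purpose is safety under repeated intermittent use over 6 months. A child who has a new event on day 10 after a dose has a non-treatment-emergent event. It is placed in Part 2, has no dose group, and enters no summary that the SAP specifies. Nothing exempts SAEs or deaths.

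The incidence shown in the Part 2 tables would therefore describe tolerability close to dosing. Events between attacks would have to be counted by hand from listings, with no denominator by dose.

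The plan treats other data differently. Section 2.2 attributes post-baseline findings to the last dose before the visit, and concomitant medications to the dose taken before they were started, with no limit in days. Section 6.4 counts Part 2 concomitant medications from Visit 4 onward. A medicine started for that day-10 event would be tabulated by dose while the event itself would not.

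**Working it through.** The SAP gives no figure for the share of the extension inside the TEAE window, so there is none to reproduce.

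**Inputs**
- Days covered per attack, single dose: dosing date plus 3 days = 4 calendar days (6.1.5).
- Days covered per attack with the second-dose extension: 4 + 3 = 7 (6.1.5).
- Length of follow-up: 6 months of 30 days = 180 days from Visit 4 (6.8).
- Attacks per month: an average of 1 as the floor in the planning target (1.2), 4 as the permitted maximum (1.1). Actual frequency is not given, so the range between them is an assumption.

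**Formula**

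Share outside = 1 − (6 × attacks per month × days per attack) / 180.

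Windows are taken not to overlap, which gives the greatest possible coverage and so the smallest share outside.

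| Attacks per month | Covered, single dose | Outside | Covered, second dose every attack | Outside |
|---|---|---|---|---|
| 1 | 6 × 1 × 4 = 24 days | 86.7% | 6 × 1 × 7 = 42 days | 76.7% |
| 2 | 48 days | 73.3% | 84 days | 53.3% |
| 3 | 72 days | 60.0% | 126 days | 30.0% |
| 4 | 96 days | 46.7% | 168 days | 6.7% |

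**Overlap.** A simulation with random attack timing, attacks at least 3 days apart, gave coverage at 4 attacks per month of 51.5% (single doses) and 74.6% (extended). The shares outside become 48.5% and 25.4%. At 1 attack per month overlap hardly matters: coverage is 13.2% and 22.1%.

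**Break-even.** Half of follow-up is covered when 6 × rate × days per attack = 90. That gives 90 / (6 × 4) = 3.75 attacks per month with single doses, and 90 / (6 × 7) = 2.14 with the extension on every attack.

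**At the planning floor.** Fifty completers give 50 × 180 = 9,000 person-days. With one single-dose attack a month, 50 × 24 = 1,200 are inside the window and 7,800 (86.7%) outside.

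**Below the floor.** Section 3.2.1 has an exposure category for fewer than 4 doses. Three single-dose attacks cover at most 3 × 4 = 12 of 180 days, leaving 93.3% outside.

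**Worsening of earlier illness.** Section 6.1.5 counts it as a TEAE with no day limit. Section 6.1.6 says that every TEAE, by definition, falls within 3 days of a dose or the second-dose extension, and uses that dose to assign study part and treatment group. A worsening that starts on day 10 is a TEAE under the first and cannot be assigned under the second.

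**The case against.** The case against has several parts.

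- **The long-term safety question.** A reader might infer that the extension leaves it unanswered. The document does not support that. Part 2 summaries of laboratory values, vital signs, ECG, C-SSRS and physical findings (6.2 to 6.7) are tied to visits, not doses. Reasons for early discontinuation are tabulated for each part with no TEAE restriction (3.1). This stands.
- **Late events are not lost.** They are collected, assigned to Part 2 and listed, and SAEs are reconciled with the safety database. This stands, but a listing gives no incidence.
- **Most of the follow-up.** A reader might infer that most of it always falls outside the window. That fails at high use: with 4 attacks a month and second doses throughout, only 6.7% is outside. One attack per month is a floor in Section 1.2, not an expected rate.
- **The second-dose extension.** A reader might infer that it contradicts 6.1.6. It does not, because 6.1.6 allows for it in parentheses. The added 3 days are also coherent with a second dose that may come up to 72 hours after onset. Running the window from the second dose instead would shorten it when both doses fall on one date, from 7 days to 4.
- **The table shells.** Section 2.2 refers to a separate shells document for the treatment groups in each table. It is not available here and might contain an SAE, death or all-event table. That cannot be excluded, but the SAP text commits to none.
- **Design choice.** Tying TEAEs to doses is reasonable for a drug taken only for attacks. Agreed, and the TEAE table should stay.

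**Conclusion.** The point holds as a gap in the specified adverse event summaries. For new events starting after the TEAE window, the SAP text provides assignment to a study part and a listing, but no table and no treatment group. This includes SAEs and deaths, although the heading of 6.1.7 names deaths.

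At the planning floor of 1 attack per month, 76.7% to 86.7% of the 180 days is outside the window. At 4 attacks per month it is 6.7% to 46.7%. In each range the lower figure assumes a second dose for every attack and the higher assumes none. All four rest on non-overlapping windows and assumed attack frequencies. They measure follow-up time in which a new event cannot be a TEAE, not the number of events that will be missed.

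Separately, 6.1.5 and 6.1.6 disagree on whether a late worsening of earlier illness can be a TEAE. The text supports no broader conclusion about the extension's safety evaluation.

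**What to change.** 1. Keep the TEAE definition's window, including the second-dose extension, and the TEAE table as they are.
2. In 6.1.7, add for Part 2 an incidence table of all adverse events with onset from the first OLE dose to end of study, grouped by the dose last taken before onset. This is the last-dose logic that 2.2 already applies to findings. Amend 6.1.6 so that non-treatment-emergent events can be grouped this way for that table.
3. In both parts, tabulate SAEs, deaths and adverse events leading to discontinuation regardless of time since dose.
4. Reconcile 6.1.5 with 6.1.6: state whether worsening of earlier illness is bound by the window and, if not, how such an event is assigned to a study part and dose.

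The cost is SAP wording and a few extra tables from data already collected. The drawback is that background events unrelated to dosing will enter the all-event table. The unchanged TEAE table beside it lets the reader separate the two.
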